Interleaved TMS-fMRI for Hippocampal Stimulation: Modeling Dose-Response Relationship in Amnestic Mild Cognitive Impairment

March 25th, 2025

NCT05515952

[figure not shown]
Approach

Participants

Thirty-eight right-handed individuals with aMCI (50-80 years old) will be enrolled in this study. The following revised Mayo clinic criteria for MCI¹ will be used for the inclusion of individuals with MCI: (a) self- or informant-reported cognitive complaint; (b) objective cognitive impairment; (c) preserved independence in functional abilities; and (d) absence of dementia. The MCI diagnosis will be supported by the measures of general cognitive function using Mini-Mental State Exam (MMSE) 24-27 (inclusive); (2) Montreal Cognitive Assessment (MoCA) 18-26 (inclusive); and (3) Clinical Dementia Rating Scale score of 0.5. Only individuals with aMCI (i.e., memory is significantly impaired) will be included in the study. The Jak/Bondi actuarial neuropsychological test method² and NACC UDS 3.0 Neuropsychological battery³ will be used to identify aMCI (i.e., 1 standard deviation below the mean for their age and education matched peers on normative data in at least 2 tasks of the memory domain²). A web-based normative calculator will be used to estimate the level of performance (i.e., Z score and percentile) on each NACC UDS measure⁴. We will not include individuals with unstable medical condition, contraindications to MRI and TMS, clinical evidence of stroke, psychiatric disorder, and other neurological disorders or head injury.

[figure not shown]
Trial design

Thirty-eight individuals with aMCI will be enrolled in the 3-day interleaved TBS-fMRI study. Participants will be randomly assigned into one of the two TBS groups: active TBS or sham TBS (Figure 1). Participants will receive 3 TBS sessions on day 2 with each TBS session separated by 60 minutes to maximize the TBS effect^{5,6}. Participants in the active TBS group will receive 3 excitatory TBS sessions (the 3 yellow ovals in Figure 1). Participants in the sham TBS group will undergo a procedure identical to the active TBS except that no TBS will be provided (the 3 white ovals in Figure 1). Research participants and outcome assessors will be blinded for participants' allocated group. Outcome measures assessing memory function, hippocampal functional connectivity, and hippocampal activation during a memory task will be acquired on day 1 (baseline), day 2 (immediate effect), and day 3 (lasting effect). We hypothesize that active spaced TBS will enhance memory function, strengthen hippocampal functional connectivity, and increase hippocampal activation compared to the sham TBS immediately and 24 hours after the last TBS session.

Outcome measures

Accuracy of the face-name associative memory (FNAME) task, resting-state hippocampal functional connectivity, and hippocampal activation pattern will be the primary outcome measures. Participants will perform the FNAME task, which was adapted from previous paradigm^{7,8}, inside the MRI scanner. The FNAME task consists of both encoding and retrieval phases (Figure 4). During the encoding phase, participants will be instructed to remember the name that goes with each face and make a subjective decision as to how well each name fits the corresponding face (a strategy designed to augment associative encoding)⁹. Encoding phase will be divided across 4 functional runs, each consisting of 16 face-name pairs (display duration = 5.5 sec for each pair), interspersed with fixation trials (duration = 0.5-12.5 sec), yielding a total of 64 face-name pairs. Following encoding with a 5-min break, participants will

be presented with 3 types of face-name pairs (correct face-name pairs, incorrect face-name pairs, or new face-name pairs) inside the MRI scanner during the retrieval phase. There are 4 functional runs, each consisting of 10 correct, 6 incorrect, and 6 new face-name pairs interspersed with fixation trials, yielding a total of 88

face-name pairs. Accuracy will be measured as the number of right responses (e.g., Figure 4 face-name pairs B-D) relative to the total number of face-name pairs shown during the retrieval phase. We created 8 versions of the face-name tasks. Our pilot data from 20 healthy adults indicated excellent parallel-forms reliability across the 8 test versions (ICC = 0.93, 95%CI = [0.88, 0.97]). The administration order of different versions will be randomized across the participants. The score of the FNAME task has been found to be correlated with beta amyloid burden⁷, reduced hippocampal volume, and APOE4 carrier status in cognitively normal older adults¹⁰. The FNAME task is sensitive to longitudinal clinical decline in MCI¹¹ and in those at genetic risk for AD¹²⁻¹⁴.

Statistical design and analysis

This study employs a parallel group design with 2 groups (active TBS and sham TBS) and 3 primary data collection time points (day1, day 2, and day 3). Participants will be randomized to one of the 2 groups using a randomization scheme stratified on age (50-65 vs. 66-80) and sex. For the accuracy of the FNAME task, a linear mixed effects model will be fit to the accuracy scores from the FNAME task to look at the change in accuracy over time for both the active and sham TBS groups. The model will include fixed predictors for time (3 levels: day 1, day 2, and day 3), group (2 levels: active TBS and sham TBS), their interaction, age, sex, and education. A

random intercept per participant will be included to account for the potential correlation among data from the same participant.

1. Petersen, R. C. *et al.* Mild cognitive impairment: a concept in evolution. *J Intern Med* **275**, 214-228 (2014). <https://doi.org/10.1111/joim.12190>
2. Jak, A. J. *et al.* Neuropsychological Criteria for Mild Cognitive Impairment and Dementia Risk in the Framingham Heart Study. *J Int Neuropsychol Soc* **22**, 937-943 (2016). <https://doi.org/10.1017/S1355617716000199>
3. Weintraub, S. *et al.* Version 3 of the Alzheimer Disease Centers' Neuropsychological Test Battery in the Uniform Data Set (UDS). *Alzheimer Dis Assoc Disord* (2017). <https://doi.org/10.1097/WAD.0000000000000223>
4. Shirk, S. D. *et al.* A web-based normative calculator for the uniform data set (UDS) neuropsychological test battery. *Alzheimer's research & therapy* **3**, 32 (2011). <https://doi.org/10.1186/alzrt94>

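### Does a title that promises dose-response modelling oblige the plan to contain a dose analysis?

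*Combined protocol and SAP*

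**What the plan says.** The title presents the study as "Modeling Dose-Response Relationship in Amnestic Mild Cognitive Impairment". The word dose does not recur in the readable text.

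Under Trial design there are two randomised arms: "Participants will be randomly assigned into one of the two TBS groups: active TBS or sham TBS". Exposure is uniform within each arm. "Participants in the active TBS group will receive 3 excitatory TBS sessions", all on day 2 and an hour apart. The sham procedure is the same "except that no TBS will be provided (the 3 white ovals in Figure 1"). Outcomes "will be acquired on day 1 (baseline), day 2 (immediate effect), and day 3 (lasting effect"). The hypothesis for activation is that active stimulation will "increase hippocampal activation compared to the sham TBS immediately and 24 hours after the last TBS session", and the memory and connectivity hypotheses take the same form.

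Under Statistical design and analysis, the one written model, for FNAME accuracy, has "fixed predictors for time (3 levels: day 1, day 2, and day 3), group (2 levels: active TBS and sham TBS), their interaction", plus age, sex, education and a participant random intercept.

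Three details bear on what else might be measured. The study is described as one in which participants are "enrolled in the 3-day interleaved TBS-fMRI study". The three time points are called primary. Eight parallel versions of the memory task exist, against three named days.

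**The concern.** A title usually states the purpose of a trial. A reader who meets this one expects several dose levels, a definition of dose and a model relating response to it. The readable text supplies none of these. Every active participant is due the same number of sessions, every sham participant none, and the outcome days fall before and after the whole block of stimulation.

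The risk lies in reporting. A dose-response statement could appear under this title with no analysis in this document behind it. If scans between sessions were collected, the choice of region, contrast and functional form could be made with the data in view.

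**Working it through.** The documents give no numerical claim on dose to reproduce, so the check is of what the written design and model can estimate.

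**Inputs.** From Trial design: two arms, three sessions in the active arm, none in the sham arm, outcomes on days 1, 2 and 3. From Statistical design and analysis: the fixed effects. Assumptions: dose means cumulative active sessions *S*; the day 2 outcome follows the third session, as the hypothesis implies; 38 participants are split 19 per arm (no ratio is stated, and the ranks below do not depend on it).

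**Step 1: dose values at the written time points.** Sham: 0, 0, 0. Active: 0, 3, 3. There are two distinct values, 0 and 3.

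**Step 2: the written model.** With *G* = 1 for active, and *D2* and *D3* marking days 2 and 3, the mean is

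*b0 + b1·G + b2·D2 + b3·D3 + b4·G·D2 + b5·G·D3* + age, sex and education terms.

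That is 1 + 1 + 2 + 2 + 3 = 9 columns, rank 9. Here *b4* is the active-minus-sham difference in change from day 1 to day 2, and *b5* the same for day 3. These match the two parts of the hypothesis.

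**Step 3: add dose.** *S* = 3·(*G·D2* + *G·D3*). The rank stays at 9, so the term carries no new information.

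**Step 4: let dose replace the interaction.** The model without interaction has 9 − 2 = 7 columns, rank 7. Adding *S* gives rank 8. Adding *S*² leaves it at 8, because *S* takes only the values 0 and 3 and so *S*² = 3·*S*. One contrast of 0 with 3 sessions is estimable, and no curvature. This version also forces *b4* = *b5*, which discards the distinction between immediate and lasting effect that the protocol wants.

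**Step 5: is the redundancy in Step 3 itself the fault?** Suppose outcomes were also taken after each session, giving the active arm 0, 1, 2, 3, 3. The group-by-time model then has 1 + 1 + 4 + 4 + 3 = 13 columns, rank 13, and adding *S* leaves it at 13. Yet shape is estimable in that design: without the interaction the rank is 9, rising to 10 with *S* and 11 with *S*². A dose fixed by arm and time is always redundant in a saturated group-by-time model, whether the design is informative about dose or not. The real limit is having only two dose values at the written time points.

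**Step 6: text against text.** The title names dose-response. The hypothesis, arms, outcome days and model all name active versus sham. The body agrees with itself, and only the title stands apart.

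**The case for a change.** The strongest case for a change is that the remedy is cheap and the mismatch plain. Define dose; if scans between sessions exist, write down one secondary model; if they do not, reword the title. Neither route needs participants, visits or a different stimulation schedule. The missing figure does not answer the point, since the statistics section is readable and has no dose term. If session-level data are being gathered, the case for fixing the analysis early is stronger.

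Much of this stands. The title is not matched by the readable plan, and a missing figure cannot supply a model. Three things weaken it as a ground for change.

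- A secondary model would be written for data not shown to exist. The interleaved design, the word primary and the eight task versions are compatible with measurement between sessions but do not establish it.
- Sessions are only one meaning of dose. If intensity or field at the target is meant, the session-count argument does not apply, and the readable text offers no variable to model instead.
- Even with scans at each session, session number is not randomised and rises with elapsed time. A delayed effect of the first session could not be told apart from an effect of later ones, so the analysis would be exploratory.

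Nor does the absence of a dose analysis from so short a document show that one would be chosen only after the data are seen.

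**Conclusion.** The observation is correct, but no change to the plan is needed. Followed as written, the plan yields the active-versus-sham contrasts on day 2 and day 3 for FNAME accuracy, which is what the hypothesis asks, and their validity does not depend on the title. On the sessions reading there are two dose values, 0 and 3, and no information on shape. A dose term would add nothing to the written model, or would merge two contrasts that should stay separate.

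This is a gap that analysts can fill sensibly: they report active versus sham, and label any account of response by session or intensity as exploratory unless its analysis was fixed in advance. The body makes no dose-response claim that has to be withdrawn.

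The conclusion rests on the readable text. The session-count result further assumes that dose means sessions and that outcomes are taken only at the three named time points. If Figure 1 shows measurements between sessions, more could be learned about accumulation across sessions, but the active-versus-sham comparison would be unchanged.

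### Does the short description of the sham undermine the claim that participants are blinded?

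*Combined protocol and SAP*

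**What the plan says.** All the relevant wording on sham and blinding is in the Trial design section of the combined protocol and SAP. For the active arm: "Participants in the active TBS group will receive 3 excitatory TBS sessions". On timing: "Participants will receive 3 TBS sessions on day 2 with each TBS session separated by 60 minutes". For the comparator: "Participants in the sham TBS group will undergo a procedure identical to the active TBS except that no TBS will be provided", with a reference to the white ovals in Figure 1. The sentence after that reads "Research participants and outcome assessors will be blinded for participants' allocated group".

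Under Outcome measures there are three primary outcomes: accuracy on the face-name memory task (FNAME), and "resting-state hippocampal functional connectivity, and hippocampal activation pattern will be the primary outcome measures". On FNAME scoring: "Accuracy will be measured as the number of right responses", taken relative to all pairs shown at retrieval (88). Measurements "will be acquired on day 1 (baseline), day 2 (immediate effect), and day 3 (lasting effect").

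The Statistical design and analysis section describes a parallel-group comparison. Its FNAME model has terms for time, group, their interaction, age, sex and education, plus a random intercept. It has no term or side analysis concerning blinding.

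**The concern.** Taken word for word, the sham sentence makes delivery of TBS the one difference between the arms. If delivered TBS can be heard or felt (an assumption; the document is silent), those cues would be absent from the sham arm in all three day-2 sessions. The next sentence claims participant blinding without saying how it is achieved.

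The stake would be the active-sham contrast itself. FNAME accuracy comes from the participant's own responses, and hippocampal activation is recorded during a memory task. Both could move with effort or expectation, and both are measured on day 2 and again on day 3. A participant who had guessed the arm would carry that belief into them. Blinded assessors cannot remove such an effect, and the FNAME model cannot separate it from an effect of stimulation. Resting-state connectivity is less exposed.

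It is therefore natural to ask for a masking description, a guess question at the end of day 3, and possibly a weaker claim about the level of blinding.

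**Working it through.** The plan gives no figure on blinding to reproduce, so the first step is to set the sentences side by side.

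**Text check**

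| Item | Sentences in the visible text |
|---|---|
| Describes the sham | 1 |
| States that participants are blinded | 1 |
| Says how sound or sensation is matched or masked | 0 |
| Plans a check of blinding | 0 |

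Two readings fit the sham sentence.

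- *Reading A.* The sham reproduces the session, including what is heard and felt, without effective stimulation. The blinding sentence then follows directly.
- *Reading B.* Nothing at all is delivered, so the sessions are silent and without sensation. The blinding claim then depends on whether a participant could tell. Nobody receives both conditions in a parallel design, so there is no direct comparison to give the arm away. Inference would depend on earlier experience of TMS and on what participants are told, and the text states neither.

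Reading A is the one under which both sentences hold without further assumptions. Reading B is possible, but nothing in the text establishes it.

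**What a guess question would add**

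Inputs: n = 38 from the Trial design section. Assumptions: everyone answers, there are 19 per arm, and the true correct-guess rates are as shown.

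Pooled exact binomial test of X ~ Bin(38, p) against p = 0.5, two-sided 0.05:

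- Reject if X ≤ 12 or X ≥ 26 (26/38 = 68%). The actual size is 3.4%. Moving the upper cut-off to 25 (and the lower to 13) would give 7.3%, so 26 is the right limit.
- Probability of rejection at each true rate:

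| True correct-guess rate | Probability of rejection |
|---|---|
| 60% | 18.7% |
| 65% | 39.9% |
| 70% | 65.9% |
| 75% | 86.8% |
| 80% | 97.1% |

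These figures describe a pooled test. The sensible way to report guesses is by arm, and the pooled test can mislead:

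- If 80% in both arms guess active, the correct rates are 0.80 (active) and 0.20 (sham). Pooled accuracy is (0.80 + 0.20)/2 = 50%, and the test rejects 0.8% of the time.
- If 70% of the active arm and 50% of the sham arm are correct, it rejects 18.1% of the time.

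The per-arm blinding index is 2p − 1. Its 95% half-width at p = 0.5 with 19 per arm is 1.96 × 2 × √(0.25/19) = 0.45, on a scale from −1 to 1.

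The question would thus detect gross unblinding and little else.

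**The case for a change.** The strongest case for a change is that it is nearly free. One sentence on what sham participants hear and feel, and one question after the last day-3 assessment, would need no extra visit and could not influence the outcomes. The check is strong against gross unblinding (97% detection at an 80% correct-guess rate), which is the risk if nothing is delivered. Any masking detail in Figure 1 would not supply a blinding check, because the outcome and analysis sections mention none.

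Part of this stands. The visible text does not say how participant blinding is achieved, and a report of the trial should. FNAME scores and task activation are also the outcomes where lost blinding would matter most.

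The rest does not carry a change:

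- The extra sentence would write down a sham method that the sponsor presumably already has; it would alter neither the design nor the analysis.
- Calling the trial assessor-blind would require showing that sham participants notice nothing and can infer their arm. Neither is shown.
- The guess would come after all outcomes, be reported descriptively and stay out of the analysis, so no planned estimate would move. It may also partly reflect how well participants think they performed.
- FNAME is scored on right answers, not self-report, and the document offers nothing from which to size an expectation effect on it.

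**Conclusion.** No change to the plan is needed. The concern identifies a gap in reporting, and nothing in the text shows that blinding will fail. The two sentences agree if the sham is sensory-matched, which is a natural reading of them together.

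The size of any bias cannot be estimated from the documents. The numbers above measure only the proposed check: 19% detection at a 60% correct-guess rate, 97% at 80%, and a per-arm index known to about ±0.45.

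The conclusion assumes that the sponsor's sham reproduces the session well enough to support the stated blinding. The text neither confirms nor contradicts this, and Figure 1 and the consent pages, which might describe the sham, could not be read. If sham participants in fact heard and felt nothing, the claim of participant blinding would need a fresh look. The team can describe the sham experience when reporting the trial, and an allocation guess reported by arm is optional.

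### Does pooling correct, incorrect and new pairs into one FNAME accuracy score call for a prespecified split by pair type?

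*Combined protocol and SAP*

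**What the plan says.** The Outcome measures section makes task accuracy one of three primary outcomes: "Accuracy of the face-name associative memory (FNAME) task, resting-state hippocampal functional connectivity, and hippocampal activation pattern will be the primary outcome measures". Encoding uses four runs of 16 pairs, "yielding a total of 64 face-name pairs". For retrieval, "There are 4 functional runs, each consisting of 10 correct, 6 incorrect, and 6 new face-name pairs"; the section gives the retrieval total as 88. The score is defined as "Accuracy will be measured as the number of right responses (e.g., Figure 4 face-name pairs B-D) relative to the total number of face-name pairs" presented at retrieval.

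Under Statistical design and analysis, "a linear mixed effects model will be fit to the accuracy scores from the FNAME task". Its fixed terms are day, arm, the day-by-arm interaction and three baseline covariates. The text gives no score by pair type, no discrimination index and no pair-type term.

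The behavioural hypothesis, under Trial design, is general: "We hypothesize that active spaced TBS will enhance memory function". Figure 4, which illustrates the responses, is not reproduced in the text available here.

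**The concern.** The task is called associative, and the encoding instruction is meant to strengthen associative encoding. Yet a new pair can be rejected without knowing which name went with which face, and such pairs make up more than a quarter of the score. Studied pairs are also unbalanced, 40 correct to 24 incorrect, so a greater readiness to answer *correct* can raise the total with no change in memory.

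A positive day-by-arm effect might therefore be reported as improved associative memory when it came from novelty rejection, or the reverse. The responses already collected could help to separate the two, but a split chosen after unblinding would be post hoc. Hence the suggestion to prespecify an associative d' and proportions right by pair type.

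**Working it through.** **Counts (Outcome measures).** 4 × (10 + 6 + 6) = 40 + 24 + 24 = 88, which reproduces the plan's total. The shares are 40/88 = 45.5%, 24/88 = 27.3% and 24/88 = 27.3%. Also 40 + 24 = 64 = 4 × 16, the number of encoded pairs. This suggests, but does not state, that incorrect pairs recombine studied faces and names.

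**Same score, different memory.** Pooled accuracy = (right on correct + right on incorrect + right on new)/88. Take 30 of 40 correct pairs right.
- 6 incorrect and 24 new right: (30 + 6 + 24)/88 = 68.2%.
- 18 incorrect and 12 new right: (30 + 18 + 12)/88 = 68.2%.

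Suppose every error on an incorrect pair was a *correct* response. Then d' = z(30/40) − z(false-alarm rate):
- First case: z(0.75) − z(18/24) = 0.00.
- Second case: z(0.75) − z(6/24) = 1.35.
- With log-linear correction: z(30.5/41) − z(18.5/25) = 0.01 and z(30.5/41) − z(6.5/25) = 1.30.

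**Same gain, different source (assumed rates).** Start at 65% right on correct, 55% on incorrect and 50% on new pairs: (26 + 13.2 + 12)/88 = 58.2%.
- New pairs rise to 80%: (26 + 13.2 + 19.2)/88 = 66.4%.
- Both studied types rise by 11.25 points instead: (30.5 + 15.9 + 12)/88 = 66.4%.

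**Response bias (assumed rates).** Take zero association and 60% right on new pairs. Raising the rate of calling studied pairs *correct* from 50% to 80% moves the score from (20 + 12 + 14.4)/88 = 52.7% to (32 + 4.8 + 14.4)/88 = 58.2%.

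**What a split costs in precision.** At an assumed 60% accuracy, the binomial standard error per participant and session is:
- all 88 pairs: √(0.24/88) = 0.052;
- 40 pairs: √(0.24/40) = 0.077;
- 24 pairs: √(0.24/24) = 0.100;
- difference between the 40-pair and 24-pair proportions: √(0.24/40 + 0.24/24) = 0.126.

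**Simulation.** The document gives no performance figures, so every performance input is assumed: 19 per arm, d' mean 0.8 (SD 0.4), criterion mean 0 (SD 0.3), an equal-variance normal model, and the day-2 contrast of a random-intercept model tested two-sided at 5%.
- New-pair rejection rising from 70% to 85% adds 24/88 × 15 = 4.1 points. A d' gain of 0.33 adds the same.
- Pooled accuracy shows benefit in 45.3% and 44.7% of trials respectively. The routes were matched on the gain, so near-equality is built in and is not separate evidence.
- Given a pooled benefit, d' also shows benefit in 5.7% (novelty route) against 86.4% (association route). With day-to-day SD 0.3 the figures are 8.8% and 76.9%.
- A smaller novelty effect, 70% to 75%, makes pooled accuracy favour active in only 8.7% of trials (5.9% with day-to-day variation), against 2.5% by chance.
- Criterion shifts of 0.10 to 0.15 make pooled accuracy significant in 5.2% to 9.4% of trials, little above 5%.
- The d' effect has standard error 0.157, or 0.21 with day-to-day variation. With 72 error df the 95% half-width is 1.99 × 0.157 = 0.31, or 1.99 × 0.21 = 0.42.
- If association and novelty rejection both improve (d' +0.4, rejection 70% to 80%), d' is significant in 68.5% of trials and pooled accuracy in 92.5%. With day-to-day variation these are 45.0% and 64.4%. Among trials with a pooled benefit, d' misses the true gain in about 26%, or 36% with day-to-day variation.

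**The case for a change.** The strongest case for a change is that it is nearly free. It needs no new data, leaves the primary test alone, and fixes the split before anyone sees unblinded results. A positive result on a task with this name will readily be read as an associative gain, and no stated analysis would support or refute that reading. The simulation shows that d' can tell the two routes apart when the novelty effect is large.

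Much of this stands. The pooled score cannot identify the source of a gain, and a later split would carry less weight than a prespecified one. But the harm lies in how a future report might be worded, because the document plans no claim narrower than memory function. The quantitative case rests mainly on one assumed mechanism, a selective 15-point rise in novelty rejection with no associative change, and nothing in the document makes that likely.

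The only part that would alter a conclusion is the rule that an associative claim needs support from d'. What counts as support is undefined; if it means significance, d' becomes a second test in all but name. It would also withhold a true claim at the rates shown above. The index isolates association only if incorrect pairs recombine studied items. It can be disturbed as well: d' is significant in 12.0% of simulated trials when studied pairs wrongly called new fall from 30% to 10% in the active arm and new-pair accuracy falls from 85% to 75%. The response options may be shown in Figure 4, so their absence from the available text cannot be counted as an omission.

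**Conclusion.** No change to the plan is needed. The pair counts are right, and the limit on interpretation is real: up to 27.3 points of the score depend on unstudied pairs, and a single total of 68.2% fits an associative d' anywhere from 0.00 to 1.35 in the worked example. Even so, the planned active-versus-sham comparison is a valid test of overall recognition accuracy, which is a fair measure of the hypothesised memory function. Splitting the score corrects no bias, error rate or power in that comparison.

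If the investigators later want the narrower associative claim, they could report proportion right by pair type. They could add a discrimination index on the 64 studied pairs, with its confidence interval, provided Figure 4 confirms that incorrect pairs are recombined studied items. Both would be descriptive, without a significance gate. The counts and the pooling come directly from the text. The simulated percentages rest on assumed performance, variability and response format, and indicate scale only.

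### The FNAME accuracy model has no term for test version; a random version intercept costs almost nothing and gives a precision gain of unknown size, from nil to moderate

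*Combined protocol and SAP*

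**What the plan says.** The combined protocol and SAP, under Outcome measures, makes FNAME accuracy one of three primary outcomes. On the test forms it states: "We created 8 versions of the face-name tasks". It then reports: "Our pilot data from 20 healthy adults indicated excellent parallel-forms reliability across the 8 test versions (ICC = 0.93, 95%CI = [0.88, 0.97" (closing brackets omitted). On assignment of forms it says only: "The administration order of different versions will be randomized across the participants".

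Under Statistical design and analysis there are "3 primary data collection time points (day1, day 2, and day 3"). The linear mixed model for FNAME accuracy has fixed effects for time, group, time by group, age, sex and education. For the random part, a "random intercept per participant will be included to account for the potential correlation among data from the same participant". Version is in neither part. Allocation is described as: "Participants will be randomized to one of the 2 groups using a randomization scheme stratified on age (50-65 vs. 66-80) and sex".

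The documents do not give the type of ICC, the version means, the between-version variance, or whether version order is balanced by arm or day.

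**The concern.** Parallel versions are presumably used so that participants do not meet the same material on successive days. The consequence is that each day-to-day change in a participant's score also contains the difference in difficulty between two versions. The participant intercept cannot absorb that difference, because it varies within the participant. With no version term it goes into the residual, and the day-2 and day-3 group contrasts are judged against that residual.

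The ICC of 0.93 looks reassuring but answers a different question. It compares non-person variance with between-person variance, whereas the group-by-time contrast removes between-person variance. What matters is the share of within-person variance that is due to version, and the ICC does not give that share. With 38 participants, precision that can be had cheaply is worth taking.

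**Working it through.** **Inputs from the documents.** 38 participants, 2 groups, 3 days, 8 versions; pilot ICC 0.93 (95% CI 0.88 to 0.97) in 20 healthy adults.

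**Assumptions.** 19 per arm; one version per day, so each participant sees 3 of the 8; complete data; two-sided 5% level. None of these is stated. Age, sex and education are constant within a person and do not affect the within-person contrasts, so they are left out.

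**1. The plan's own figure.** For a single-measure ICC with n = 20 and k = 8, assuming every pilot participant took every version:

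- F = (1 + 7 × 0.93)/(1 − 0.93) = 7.51/0.07 = 107.3.
- Lower limit: F/1.833 = 58.5, and (58.5 − 1)/(58.5 + 7) = 0.878.
- Upper limit: F × 2.197 = 235.7, and (235.7 − 1)/(235.7 + 7) = 0.967.

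This reproduces 0.88 to 0.97. It does not settle the ICC type: an average-measures ICC near 0.935 also rounds to the stated interval.

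**2. What the ICC allows.** Set person variance to 1. Non-person variance in the pilot is then 0.07/0.93 = 0.0753. Let s be the share of within-person variance due to version.

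- Consistency ICC: version means are removed before the ICC is formed, so it sets no bound on s.
- Single-measure absolute-agreement ICC: the McGraw-Wong interval widens as s grows. A lower limit of 0.88 fits s up to about 0.30 after rounding; at s = 0.40 the lower limit is already 0.86 to 0.87.

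**3. Variance of the group-by-time contrast.** Under the planned model, with within-person variance w, it is 2 × 2w/19 = 4w/19. With w = 0.0753 this is 0.0159. Under random version order it averages about this value whatever s is, so the planned standard error is right on average. In simulation (400 trials per setting, s from 0 to 0.5), the planned model rejected a true null in 3.8% to 6.2% of trials.

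With a crossed random version effect, generalised least squares over 300 random version orders gives the ratio R of the new variance to the planned one. Last column: power if the planned model had 80%, from Φ(2.80/√R − 1.96). The documents give no power calculation, so 80% is only a benchmark.

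| s | R | Fall in variance | Power |
|---|---|---|---|
| 0 | 1.00 | 0% | 80.0% |
| 0.10 | 0.948 | 5% | 82.1% |
| 0.20 | 0.864 | 14% | 85.4% |
| 0.30 | 0.762 | 24% | 89.4% |

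If version effects were known exactly, R would be 1 − s (0.90, 0.80, 0.70). The table is less favourable because they must be estimated from the trial.

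**4. Cost of the term if versions are equal (s = 0).** With the variance estimated by REML, the empirical variance ratio was 1.01, and rejection under the null was 6.2% without the term and 7.0% with it. The simulation standard error is √(0.05 × 0.95/400) = 1.1 percentage points, so the two do not differ noticeably. Seven fixed version effects would instead raise the variance by about 10% at s = 0 and break even near s = 0.10.

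**5. Carrying the pilot over to aMCI.** Day-to-day variation in the trial may well exceed the pilot's. Suppose residual variance is 0.3 (person variance 1), against about 0.8 × 0.0753 = 0.06 in the pilot at s = 0.20.

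- Pilot share 0.20: version variance 0.2 × 0.0753 = 0.0151; trial share 0.0151/0.3151 = 0.048; R about 0.98.
- Pilot share 0.30: version variance 0.0226; trial share 0.0226/0.3226 = 0.070; R about 0.97.

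If within-person variance merely doubles, a pilot share of 0.20 becomes 0.10 and the gain falls from 14% to 5%.

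**The case against.** The strongest case against is that the benefit may be nil. The only evidence in the documents is "excellent parallel-forms reliability across the 8 test versions (ICC = 0.93"), and no version difference is reported. Item noise points the same way. With 88 retrieval items, an assumed accuracy of 0.7 and an assumed total SD of 0.15, binomial variance is 0.21/88 = 0.0024, already above 7% of total variance (0.07 × 0.0225 = 0.0016), which leaves no room for version. At accuracy 0.9 and SD 0.20, however, 0.09/88 = 0.0010 against 0.0028 leaves about 63%. The argument is only indicative. What stands is that the gain cannot be promised.

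Four stronger readings are tempting, and the documents do not support them:

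- That version is an established source of variation. It is plausible but unquantified.
- That versions are unbalanced across arms and days. The plan is silent. Random order balances them in expectation, and a balanced list could be used. With 19 per arm, each version is expected 19/8 = 2.4 times per arm and day, so chance imbalance is likely if nothing more is done.
- That the treatment comparison is biased or its error rate inflated. Randomised order protects against the first, and step 3 shows no sign of the second.
- That the gain is large. Anything well above 24% needs a consistency ICC together with substantial version differences, and the documents give no information on either.

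**Conclusion.** The concern holds as a low-severity point about precision. The FNAME accuracy model omits a randomised design factor that can only add within-person noise, and the reported ICC does not show that noise to be negligible.

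The gain from modelling version runs from nil to about 24% of the contrast variance for shares up to 0.30. It is about 2% to 3% under the larger aMCI residual variance assumed in step 5. These figures rest on 19 per arm, one version per day, complete data and, for the 0.30 limit, a single-measure absolute-agreement ICC that carries over from 20 healthy adults. The case for the change is the near-zero cost, not a demonstrated loss. The point covers FNAME accuracy only, because the plan gives no model for the two imaging outcomes.

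**What to change.** 1. Add a random intercept for version (8 levels, crossed with participant) to the FNAME accuracy model. This is one variance parameter. Do not use fixed version effects, which cost about 10% in variance if versions are equal.
2. Where enrolment still allows, draw version order from a list balanced by arm and day, always together with item 1. Balancing removes version differences from the true variance of the contrast but leaves them in the residual of a model without version. The standard error would then be too large by roughly 1/√(1 − s), about 12% at s = 0.20.
3. State the ICC type, how versions are assigned, and the between-version variance if the pilot data permit. The plan does not say that every pilot participant took all eight versions.

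The cost is one line in the model specification and, if item 2 is feasible, one assignment list. No extra participants or assessments are needed.
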